11.1 Adverse Events

11.1.1 Reportable AEs

All AEs that occur after the informed consent is signed and baseline assessments are completed (including run-in) must be recorded on the AE CRF (paper and/or electronic) whether or not related to study agent.

11.1.2 AE Data Elements:

The following data elements are required for AE reporting.

- AE verbatim term
- NCI Common Terminology Criteria for Adverse Events version 4.0 (CTCAE v4.0) AE term (MedDRA lowest level term)
- CTCAE (MedDRA) System Organ Class (SOC)
- Event onset date and event ended date
- Treatment assignment code (TAC) at time of AE onset
- Severity grade
- Attribution to study agent (relatedness)
- Whether or not the event was reported as a SAE
- Whether or not the subject dropped due to the event
- Outcome of the event

11.1.3 Severity of AEs

11.1.3.1 Identify the AE using the CTCAE version 4.0. The CTCAE provides descriptive terminology (MedDRA lowest level term) and a grading scale for each AE listed. A copy of the CTCAE can be found at http://ctep.cancer.gov/protocolDevelopment/electronic applications/ctc.htm

All AEs, with the exception of changes in Pulmonary Function Tests (PFT) completed at Week 24, will be assessed according to the grade associated with the CTCAE term. Any AEs that do not have a corresponding CTCAE term will be assessed according to the general guidelines for grading used in the CTCAE v4.0. as stated below.

CTCAE v4.0 general severity guidelines:

Grade	Severity	Description
1	Mild	Mild; asymptomatic or mild symptoms; clinical or diagnostic observations only; intervention not indicated.
2	Moderate	Moderate; minimal, local or noninvasive intervention indicated; limiting age-appropriate instrumental activities of daily living (ADL)*.

Grade	Severity	Description
3	Severe	Severe or medically significant but not immediately life-threatening;
		hospitalization or prolongation of hospitalization indicated; disabling;
		limiting self-care ADL**.
4	Life-threatening	Life-threatening consequences; urgent intervention indicated.
5	Fatal	Death related to AE.

ADL

- *Instrumental ADL refers to preparing meals, shopping for groceries or clothes, using the telephone, managing money, etc.
- **Self-care ADL refers to bathing, dressing and undressing, feeding self, using the toilet, taking medications, and not bedridden.

11.1.3.2 All AEs related to changes in Pulmonary Function Tests at Week 24 when compared to baseline PFTs will be graded according to the following severity guidelines:

Grade	Severity	Description
1	Mild	Remains asymptomatic or exhibits no changes or minimal changes in pre- existing symptoms, no new related symptoms; clinical or diagnostic observation only; no changes in management; no intervention indicated.
2	Moderate	Minimal changes (worsening) in pre-existing symptoms, mild-to-moderate new related symptoms ; minimal local or non-invasive intervention indicated; limiting age-appropriate instrumental ADL**.
3	Severe	Severe or medically significant but not immediately life-threatening; hospitalization or prolongation of hospitalization indicated; disabling; limiting self-care ADL**.
4	Life-threatening	Life-threatening consequences; urgent intervention indicated.
5	Fatal	Death related to AE.

^{**}Self-care ADL refers to bathing, dressing and undressing, feeding self, using the toilet, taking medications, and not bedridden.

11.1.4 Assessment of relationship of AE to treatment

The possibility that the AE is related to study agent will be classified as one of the following: not related, unlikely, possible, probable, or definite.

If the PFT-related AE at Week 24 (as defined above) is determined to be "not related" or "unlikely," this assessment will be accompanied by a note-to-file with the rationale for such assessment.

11.1.5 Follow-up of AEs

All AEs, including lab abnormalities that in the opinion of the investigator are clinically significant, will be followed according to good medical practices and documented as such.

11.2 Serious Adverse Events

11.2.1 DEFINITION: Regulations at 21 CFR §312.32 (revised April 1, 2014) define an SAE as any untoward medical occurrence that at any dose has one or more of the following outcomes:

- Death
- A life-threatening AE
- Inpatient hospitalization or prolongation of existing hospitalization
- A persistent or significant incapacity or substantial disruption of the ability to perform normal life functions
- A congenital anomaly or birth defect
- Important medical events that may not be immediately life-threatening or result in death or hospitalization should also be considered serious when, based upon appropriate medical judgment, they may jeopardize the patient and may require intervention to prevent one of the other outcomes.

11.2.2 Reporting SAEs to DCP

11.2.2.1 The Lead Organization and all Participating Organizations will report SAEs on the DCP SAE Report Form or application found at http://prevention.cancer.gov/clinical-trials/clinical-trials-management/protocol-information-office/pio-instructions-and-tools/2012-consortia.

11.2.2.2 Contact the DCP Medical Monitor by email (preferable) or phone within 24 hours of knowledge of the event.

[name], M.D.

National Institutes of Health, National Cancer Institute, Division of Cancer Prevention

Medical and Scientific Monitor

Lung and Upper Aerodigestive Cancer Research Group

[name]

[name]

[contact] [contact]

Email: [contact]

Include the following information when calling the Medical Monitor:

- Date and time of the SAE
- Date and time of the SAE report
- Name of reporter
- Call back phone number
- Affiliation/Institution conducting the study
- DCP protocol number
- Title of protocol
- Description of the SAE, including attribution to drug

Guidance for the process of coding the SAE can be obtained by contacting the NCI MD Help Desk: [contact]

11.2.2.3 The Lead Organization and all Participating Organizations will also submit typed SAE reports and follow up reports within 48 hours of learning of the event using the DCP SAE Report Form to all of the following:

• [name]., DCP Medical Monitor

[contact]

Email: [contact]

• [name]. Principal Investigator/Study Chair

[contact]

Email: [contact]

 CPN Operations Office [contact]

Email: [contact]
 DCP's Regulatory Contractor CCS Associates, Inc.

[contact] Email: [contact]

11.2.2.4 The DCP Medical Monitor and CCSA regulatory and safety staff will determine which SAEs require FDA submission as IND safety reports.

11.2.2.5 The Lead Organization and all Participating Organizations will comply with applicable regulatory requirements related to reporting SAEs to the CIRB/IEC.

11.2.3 Follow-up of SAE

Site staff should send follow-up reports as requested when additional information is available. Additional information should be entered on the DCP SAE Report Form in the appropriate format. Follow-up information should be sent to all of the above, including DCP, as soon as available. All SAEs will be followed according to institutional standards of good clinical practice.

12. STUDY MONITORING

12.1 Data Management

The Mayo Clinic Cancer Center database will be the database of record for the protocol and subject to NCI and FDA audit. Minimum Data Sets will be submitted to DCP per contract requirements. Please see the DCP-approved CPN Master Data Management Plan.

12.2 Case Report Forms

Participant data will be collected using protocol-specific case report forms (CRF) utilizing NCI-approved Common Data Elements (CDEs). The approved CRFs will be used to create the electronic CRF (e-CRF) screens for data entry into the Mayo Clinic Cancer Center database. Amended CRFs will be submitted to the DCP Protocol Information Office for review and approval.

12.3 Source Documents

A source document is any document, form, or record where *specific participants'* data are first recorded. FDA [21 CFR 312.62 (b)] requires that the investigator "...prepare and maintain accurate case histories designed to record all observations and other data pertinent to the investigation on each individual treated with the investigational agent or employed as a control in the investigation." Among other

items, source documents include:

- Inpatient and outpatient medical records
- Progress notes
- Consults
- Nursing notes
- Pathology reports
- Radiology reports
- Medicine/radiation administration records
- Surgical reports
- Laboratory reports
- Admission forms
- Flow sheets that are signed and dated
- Protocol or study road maps
- Appointment books
- Participant diaries/calendars
- Participant-completed symptom diary/report card

12.4 Data and Safety Monitoring Plan

The DCP-approved Master DSMP, applicable to all studies within the CPN Consortium provides detailed information regarding data and safety monitoring for this study. The trial will be monitored closely for occurrence of adverse events by the study team and by the Mayo Clinic Cancer Center Data Safety Monitoring Board (DSMB). The DSMB will be consulted regarding whether or not accrual should be suspended to allow for investigation in the occurrence of severe adverse events, particularly for those that are possibly, probably, or definitely related to the study agent.

12.5 Sponsor or FDA Monitoring

The NCI, DCP (or their designee), pharmaceutical collaborator (or their designee), or FDA may monitor/audit various aspects of the study. These monitors will be given access to facilities, databases, supplies and records to review and verify data pertinent to the study.

12.6 Record Retention

Clinical records for all participants, including CRFs, all source documentation (containing evidence to study eligibility, history and physical findings, laboratory data, results of consultations, *etc.*), as well as CIRB records and other regulatory documentation will be retained by the Investigator in a secure storage facility in compliance with Health Insurance Portability and Accountability Act (HIPAA), Office of Human Research Protections (OHRP), Food and Drug Administration (FDA) regulations and guidances, and NCI/DCP requirements, unless the standard at the site is more stringent. The records for all studies performed under an IND will be maintained, at a minimum, for two years after the approval of a New Drug Application (NDA). For NCI/DCP, records will be retained for at least three years after the completion of the research. NCI will be notified prior to the planned destruction of any materials. The records should be accessible for inspection and copying by authorized persons of the Food and Drug Administration. If the study is done outside of the United States, applicable regulatory requirements for the specific country participating in the study also apply.

12.7 Cooperative Research and Development Agreement (CRADA)/Clinical Trials Agreement (CTA)

Not applicable.

13. STATISTICAL CONSIDERATIONS

13.1 Study Design/Description

This pilot study is designed to evaluate the preliminary immunogenicity of the MUC1 vaccine (as assessed at 12 weeks) and safety (up to 24 weeks of study duration) in individuals at high risk for developing lung cancer.

There are limited Quality of Life (QOL) data on participants who participate in chemoprevention trials and we intend to create a databank of QOL information by administering the "Was It Worth It" (WIWI) questionnaire at trial completion across multiple trials. We will seek to evaluate participant perception of their experience in trial participation once we have a reasonable amount of information (large enough sample size). Since participants who participate in these chemoprevention trials are high risk but otherwise healthy, the WIWI tool would help answer simple questions about participants' assessment of whether or not participation in this trial was "worth it."

13.2 Randomization/Stratification

Not applicable

13.3 Accrual and Feasibility

	DOMESTIC PLANNED ENROLLMENT REPORT Ethnic Categories					
Racial Categories	Not Hispanio	Hispanic or Latino Hispanic or L		or Latino		
	Female	Male	Female	Male	Total	
American Indian/Alaska Native	0	0	0	0	0	
Asian	1	1	0	0	2	
Native Hawaiian or Other Pacific Islander	0	0	0	0	0	
Black or African American	6	9	0	0	15	
White	8	20	2	3	33	
More Than One Race	0	0	0	0	0	
Total	15	30	2	3	50	

	INTERNATIO	INTERNATIONAL (including Canadian participants) PLANNED ENROLLMENT REPORT				
Racial Categories		Ethnic Categories				
	Not Hispanic	Not Hispanic or Latino		or Latino	Total	
	Female	Male	Female	Male		
American Indian/Alaska Native	0	0	0	0	0	

Asian	0	0	0	0	0
Native Hawaiian or Other Pacific Islander	0	0	0	0	0
Black or African American	0	0	0	0	0
White	0	0	0	0	0
More Than One Race	0	0	0	0	0
Total	0	0	0	0	0

The study design requires a total of up to 85 participants for screening evaluation with approximately 50 moving forward to registration and intervention due to anticipated screen failures of41%. We further expect up to 20% of participants to drop out or otherwise become non-evaluable by 12 weeks such that approximately 40 participants should be evaluable for the primary endpoint. We expect to enroll an average of 2-3 participants per month. With a 6-month ramp up period for participating organizations and this accrual rate, we plan to complete accrual in about 2.5 years, which includes 2 months for planned slowing of enrollment due to holidays, as well as a temporary closure in 2020 due to the COVID-19 pandemic. Accounting for participant follow-up, data entry, and analysis, the study should be completed within approximately 3.5 years.

13.4 Primary Objective, Endpoint(s), Analysis Plan

This pilot study is designed to evaluate the preliminary immunogenicity of the MUC1 vaccine (as assessed at Week 12) and the safety (assessed continually through Week 24) in individuals at high risk for developing lung cancer. The immune response to the vaccine will be evaluated by monitoring changes in IgG anti-MUC1 antibody titer ratio; defined as t12/t0, where t0 is the "initial titer" measured prior to vaccination, and t12 is the "final titer" drawn at 12 weeks. A titer ratio of ≥2 will be considered a positive response.

Immunogenicity of the MUC1 vaccine primary endpoint: The primary endpoint is the 12-week immunogenicity response where a response would be an antibody titer that is ≥2 fold higher at 12 weeks compared to baseline. The polyp trial showed a 44% response rate at week 12 compared to baseline. However, in this current study of individuals at high risk for lung cancer, we will enroll current and former smokers; thus, the population would be heterogeneous with potentially different immune response profiles. It is also likely that some spontaneous immunogenicity is generated. However, without a placebo arm, this is hard to estimate. We therefore hypothesize that around 40% of vaccinated participants will demonstrate a 2-fold or more increase in MUC1 titer at week 12 compared to pre-vaccination. A sample size of 40 evaluable participants will provide 96% power to detect an immunogenicity response rate of 15% versus 40% using a 2-sided test of proportions with a type I error rate of 0.05. With that same sample size of 40 evaluable participants, we also have sufficient power (83%) to detect an immunogenicity response rate of 20% versus 40% using a 2-sided test of proportions with a type I error rate of 0.05.

If the projected rates of screen failures and dropouts are overly optimistic, with 30 evaluable participants, we'd still have sufficient power for the primary endpoint. Specifically, a sample size of 30 evaluable participants will provide 90% power to detect an immunogenicity response rate of 15% versus 40% using a one-sided test of proportions with a type I error rate of 0.025. The primary analysis will be on all participants, without consideration of their baseline smoking status or MUC1 expression.

Safety primary endpoint: AEs and toxicities will be closely monitored for up to 24 weeks after participants receive the first dose of the MUC1 vaccine. All registered and treated participants will be evaluable for adverse events (AEs) from the time of their first dose of the vaccine. To evaluate the AE profile for this treatment, the maximum grade for each type of adverse event will be recorded for each participant and frequency tables will be reviewed to determine the overall patterns. In addition, the number and severity of adverse events will be tabulated and summarized across all grades. Grade 2+ adverse events will be similarly described and summarized separately. As per NCI CTC Version 4.0, toxicities are defined as adverse events that are classified as either possibly, probably, or definitely related to the interventional agent. Overall toxicity incidence, as well as toxicity profiles will be explored and summarized. Frequency distributions, graphical techniques, and other descriptive measures will form the basis of these analyses. In addition, we will review all adverse event data that are graded as 3, 4, or 5 and classified as either "unrelated or unlikely to be related" to the study intervention in the event of an actual relationship developing.

13.5 Secondary Objectives, Endpoints, Analysis Plans

- To explore potential differences, if any, in the immunogenicity of the vaccine (as assessed at weeks 12 and 24 by the IgG anti-MUC1 antibody titer ratio) in current vs. former smokers. We will thus continuously monitor enrollment to the trial by smoking status. Once 15 participants are enrolled, a breakdown of enrollment by smoking status will be shared with the study team. Based on the smoking status distribution, the study team will make a decision to either continue the study as is, or restrict enrollment to either the current or the former smokers in order to have at least 15 participants each within the former and current smoker categories.
- To evaluate pre-vaccination levels versus post-vaccination (Week 12) levels of circulating myeloid derived suppressor cells (MDSC) and correlate with the ability to respond to the vaccine. For this analysis, we will summarize the data using descriptive statistics and graphical methods (i.e. boxplots, scatter plots, etc.). For continuous MDSC data vs. response data, we will use t-tests or Wilcoxon Rank-Sum tests (for non-normal data). For the associations of 2 continuous variables, we will use linear regression, the correlation coefficient, and scatter plots.

In addition, as exploratory endpoints we will also assess:

- The relationship between COPD status at pre-registration and immune response in current versus former smokers. In individuals with COPD, the severity of airflow obstruction will be measured by the pulmonary function tests as per the GOLD classification
- Whether or not changes in immunogenicity in individuals with COPD corresponds to different circulating MDSC levels
- The impact of the MUC1/Poly-ICLC vaccine on inflammation-related high sensitivity C-reactive protein (hsCRP) and interleukin-6 (IL-6)
- The ability to successfully vaccinate with MUC1/Poly-ICLC vaccine depending on baseline hsCRP and IL-6 levels.

13.6 Reporting and Exclusions

All registered participants who start treatment and complete both the baseline and 12-week post-baseline evaluation will be evaluable for the 12-week immunogenicity response primary endpoint using the modified intent-to-treat principle, as long as they received the Week 0, Week 2, and Week 10

injections (See Section 5.6 for delays in vaccine administration that are considered allowable and will not impact evaluability for the primary endpoint). We plan to over-accrue by about 20% overall to ensure an adequate sample size in the primary analysis cohort. There will be no imputation for missing data. A summary and listing of all major protocol violations will be provided. All details will be given in the final study report and/or manuscript. Participants lost to follow-up will be censored on the last date of assessment (or contact) and as appropriate for analyses that are dependent upon length of study participation. All eligible participants who start treatment will be evaluable for the safety

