8. CRITERIA FOR EVALUATION AND ENDPOINT DEFINITION

8.1 Primary Endpoint

See Section 13.4.

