8.4 Off-Study Criteria

Participants may go "Off-Study" for the following reasons: development or continuation of an adverse event or serious adverse event, death, lost to follow-up, participant withdrawal, physician decision, protocol violation, completion of study, or other (with detailed comments provided). Reason(s) will be noted in the participant's research records, with the primary reason clearly identified. The participant will be classified as (Off Study/Off Agent). Data submission and follow-up after participants are determined to be a screen failure or "Off-Study/Off-Agent" for specific situations is noted below:

Ineligible: A registered participant is deemed ineligible if the participant does not satisfy each and every eligibility criterion for study entry.

- If participants received study intervention, on-study materials and all data up until the point of confirmation of ineligibility will be submitted.
- If participants did not receive study intervention, on-study materials must be submitted. No further data submission is necessary. No follow-up is required.

Major Treatment Violation: A registered participant is deemed as being in major treatment violation by the coordinating center, if the participant's very first treatment/intervention administration is so grossly administered in error, that the participant's data can no longer be used for the primary endpoint. These cases are typically rare.

• On-study material and all data up until the point of confirmation of a major violation must be submitted.

Cancel: A registered participant is deemed a cancel if he/she refuses the study before any study intervention is given.

• On-study material must be submitted. No further data submission is necessary. No follow-up is required.

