13.7 Adverse Event Stopping Rule

The trial will be monitored closely for occurrence of adverse events by the study team and by the Mayo Clinic Cancer Center Data Safety and Monitoring Board (DSMB) using the adverse event (AE) stopping rule specified below:

Adverse Event Stopping Rule: The stopping rule specified below is based on the knowledge available at study development. We note that the Adverse Event Stopping Rule may be adjusted in the event of either (1) the study re-opening to accrual after any temporary suspension or (2) at any time during the conduct of the trial and in consideration of newly acquired information regarding the adverse event profile of the treatment(s) under investigation. The study team in consultation with the Mayo DSMB may also choose to suspend accrual because of unexpected adverse event profiles that have not crossed the specified rule below.

Accrual will be temporarily suspended to this study if at any time we observe events considered at least possibly related to study treatment (i.e., an adverse event with attribute specified as "possible", "probable", or "definite") that satisfy any of the following criteria for each arm separately:

- If at any time 2 of the initial 10 treated participants or 20% of all participants (i.e. when accrual is greater than 10 participants) have experienced a grade 3 or higher adverse event.)
- Each grade 5 event will be reviewed on a case by case basis in a real time fashion to
 determine whether study accrual should be suspended. We will also review all grade 4
 adverse events regardless of attribution to monitor the emergence of any previously
 unrecognized treatment related adverse event.

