13.8 Evaluation of Response

All registered participants who start treatment and complete both the baseline and 12-week post-baseline evaluation will be evaluable for the 12-week immunogenicity response primary endpoint using the modified intent-to-treat principle, as long as they received the Week 0, Week 2, and Week 10 injections. All conclusions regarding efficacy will be based on all participants who completed both week 0 and week 12 and have immunogenicity response values from those time points as well. Participants with undetectable titers at baseline will be included in evaluation and their positive response to the vaccine will be defined as an increase in titer to at least two times the lower limit of detection of the assay.

Subanalyses may be performed on the subsets of participants, excluding those for whom major protocol deviations have been identified (e.g., early death due to other reasons, early discontinuation of

intervention, major protocol violations, etc.). However, sub-analyses may not serve as the basis for drawing conclusions concerning efficacy, and the reasons for excluding participants from the analysis should be clearly reported. For all measurements of response (i.e. the primary endpoint), the 95% confidence intervals will also be provided.

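### Section 13.6 describes the safety-evaluable group as eligible participants who start treatment, while 13.4 takes everyone registered and treated; the 13.6 wording should be aligned with 13.4

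*Combined protocol and SAP*

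**What the plan says.** Section 3 names immunogenicity and safety as co-primary endpoints. The safety population is described in two places.

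- Section 13.4, in its paragraph on the safety endpoint: "All registered and treated participants will be evaluable for adverse events (AEs) from the time of their first dose of the vaccine".
- Section 13.6, on reporting and exclusions: "All eligible participants who start treatment will be evaluable for the safety". The extracted text breaks off there. The group is named before the break, and nothing below depends on the missing words.

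Section 8.1 defines the primary endpoint only by a pointer: "See Section 13.4".

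Section 8.4 makes ineligibility a status that a registered person can have: "A registered participant is deemed ineligible if the participant does not satisfy each and every eligibility criterion for study entry". It gives separate data instructions for ineligible participants who did and did not receive the intervention. Section 8.3 also provides for participants found ineligible once treatment has begun.

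The neighbouring populations carry no eligibility condition. For immunogenicity, 13.6 starts from "All registered participants who start treatment and complete both the baseline and 12-week post-baseline evaluation" and adds receipt of all three injections. Section 13.8 repeats this and states "All conclusions regarding efficacy will be based on all participants who completed both week 0 and week 12". The stopping rule in 13.7 counts "2 of the initial 10 treated participants or 20% of all participants".

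**The concern.** The two descriptions coincide only if nobody is vaccinated and later found ineligible, and the protocol provides for exactly that case. Such a person is in the 13.4 safety population and outside the group that 13.6 names. Because 13.6 is the section on exclusions, an analyst could take its wording as one.

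Section 3 says that the safety and immunogenicity data will decide whether placebo-controlled efficacy trials follow. The trial has one arm and no blinding, so a denominator settled at analysis would be settled with the events known. A vaccinated person's adverse events belong in the safety record whether or not an entry criterion was missed. Some criteria bear on safety (ANA titer, liver tests, autoimmune disease) and others much less so (pack-years, timing of the CT scan). Exclusion could therefore be related to adverse events or unrelated to them.

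**Working it through.** **1. One person followed through each rule.** Take a registered participant who receives all three injections, completes the baseline and Week 12 evaluations, and is then found to have missed one entry criterion.

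| Section | Group named | Is this person in it? |
|---|---|---|
| 13.4, safety | registered and treated | Yes |
| 13.6, safety | eligible and started treatment | No |
| 13.6 and 13.8, immunogenicity | registered, started treatment, three injections, baseline and Week 12 done | Yes |
| 13.7, stopping rule | first 10 treated, then all participants | Yes, no eligibility condition |

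The safety wording in 13.6 is the only one of the four with an eligibility condition. Section 8.4 says that data can no longer serve the primary endpoint only for major treatment violations. It does not say so for ineligible participants.

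**2. How ineligibility can arise.** One missed criterion is enough. The numbered criteria are 6 in 4.1, 10 in 4.2, 1 in 4.3 and 2 in 4.4: 6 + 10 + 1 + 2 = 19.

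**3. The plan's own denominator.** Section 13.3 gives up to 85 screened, 41% screen failure and about 50 registered: 85 × (1 − 0.41) = 50.15, which agrees. It then allows 20% non-evaluable: 50 × (1 − 0.20) = 40, which also agrees. The safety denominator under 13.4 is therefore about 50. Under 13.6 read as an exclusion it is 50 − k, where k is the number vaccinated and later found ineligible.

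**4. Illustration.** The documents give no k, so I assume k = 1, 2 or 3. If exclusion is unrelated to adverse events, the chance that at least one of x participants with an event is dropped is 1 − C(50 − x, k) / C(50, k).

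| k | One participant with an event (x = 1) | Two participants with an event (x = 2) |
|---|---|---|
| 1 | 1/50 = 2.0% | 4.0% |
| 2 | 2/50 = 4.0% | 1 − (48 × 47)/(50 × 49) = 7.9% |
| 3 | 3/50 = 6.0% | 1 − (47 × 46)/(50 × 49) = 11.8% |

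With no assumption about the link, the reported rate can lie anywhere from (x − k)/(50 − k), floored at 0, to x/(50 − k).

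- Rare event, 1/50 = 2.0%: from 0/49 to 1/49 (0% to 2.0%) for k = 1, and from 0/47 to 1/47 (0% to 2.1%) for k = 3.
- Common event, at about the 37.5% flu-like rate that section 6.2 reports from the earlier study (19/50 = 38.0%): from 18/49 to 19/49 (36.7% to 38.8%) for k = 1, and from 16/47 to 19/47 (34.0% to 40.4%) for k = 3.

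These are limits of what is possible, not expected shifts.

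**The case against.** The strongest reply is that the two sentences do not strictly conflict. Section 13.6 says that eligible participants are evaluable. It does not say that only they are, and it names no excluded group, so an analyst who follows 13.4 breaks no sentence of 13.6. Section 8.1 also points to 13.4, where the population, the starting point and the tabulations are set out together. Eligibility is verified at pre-registration, and a signed checklist is required at registration (6.8), so such cases should be uncommon. The safety analysis is descriptive, and no test or power figure uses the denominator.

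All of this stands and limits the size of the point. It does not remove it: the exclusions section still describes the safety group by a narrower term than 13.4, and the protocol's own definitions make the difference real.

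A reader might infer more than the documents support:

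- *That the plan orders ineligible participants out of the safety analysis.* It does not. That is one reading of 13.6, and 8.1 with 13.4 points the other way.
- *That adverse event collection stops once ineligibility is confirmed.* Sections 8.3 and 8.4 ask for data up to that point but do not forbid later data. Section 8.4 releases only untreated ineligible participants and cancellations from further data and follow-up. Section 8.3 continues safety follow-up where possible, and 11.1.1 and 11.2 set no eligibility limit on reporting.
- *That the safety results would be biased in a favourable direction.* Nothing in the documents shows a direction.
- *That the stopping rule is compromised.* It carries no eligibility condition, and it already differs from the adverse event tables by design, since it counts only grade 3 or higher events at least possibly related to treatment.

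**Conclusion.** The point holds as a discrepancy in wording about the population of a co-primary endpoint. Section 13.4 is the better-supported definition, and *eligible* in 13.6 is the outlier. Read as an exclusion, it would omit a vaccinated person from the safety tables while the same paragraph does not exclude that person from immunogenicity.

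The effect is probably small. The probabilities above rest on 50 treated participants, an assumed 1 to 3 exclusions, and exclusion unrelated to adverse events. Whether that last assumption is reasonable cannot be judged from the documents. The alignment should be made, but the point does not call the design or its sample size into question.

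**What to change.** In 13.6, change the subject of the safety sentence to *All registered participants who receive at least one dose of vaccine, regardless of eligibility*, which matches 13.4. The best time is before the adverse event tables are produced.

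The cost is one phrase. No visit, sample, participant, sample size or power figure changes.

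Two additions are optional clarifications and not part of the finding. One is a sentence in 8.3 and 8.4 saying that adverse event data from continued safety follow-up of vaccinated participants are also submitted. The other is a listing of adverse events in vaccinated participants later found ineligible, beside what 13.6 already promises: "A summary and listing of all major protocol violations will be provided".
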